Severe Hypoglyce mia: the event required assistance of another person due to altered consciousness, and required another person to actively administer carbohydrate, glucagon, or other resuscitative actions. This means that the subject was impaired cognitively to the point that he/she was unable to treat himself/herself, was unable to verbalize his/her needs, was incoherent, disoriented, and/or combative, or experienced seizure or coma. These episodes may be associated with sufficient neuroglycopenia to induce seizure or coma. If plasma glucose measurements are not available during such an event, neurological recovery attributable to the restoration of plasma glucose to normal is considered sufficient evidence that the event was induced by a low plasma glucose concentration.

Definition of severe hyperglycemia/DKA:

Hyperglycemic events are classified as severe hyperglycemia or DKA if the following are present:

- Symptoms such as polyuria, polydipsia, nausea, or vomiting;
- Serum ketones > 1.0 mmol/L or large/moderate urine ketones;
- Either arterial blood pH < 7.30 or venous pH < 7.24 or serum bicarbonate < 15; and treatment provided in a health care facility

Research Blood Glucose Protocol will be followed at all times.

Research Blood Glucose Protocol:

If CGM > 180 mg/dL, patient will receive usual care based on attending physician or advanced practice professional orders based on readings from AC and HS fingerstick blood glucose readings. In other words, CGM readings will not be used for management of glucose levels > 180 mg/dL. Physicians and Advanced Practice Professionals (APPs – includes nurse practitioners or physician assistants) will be educated on the fact that, to prevent the risk of insulin stacking, CGM glucose values should not be used to bolus insulin or dose insulin. Elevated CGM readings > 180 mg/dL should not be relayed to on-call physicians or APPs by nursing staff. Pharmacy personnel will also be educated to not use CGM readings for dosing of insulin in order to prevent insulin stacking.

ii.	If CGM 100-180 mg/dL with arrow direction \smile : continue usual care
iii.	If CGM 100-180 mg/dL with arrow direction Recheck CGM in 1 hour; continue usual care
iv.	If CGM 100-180 mg/dL with arrow direction : Recheck CGM in 30 min; continue usual care
v.	If CGM 100-180 mg/dL with arrow direction (double arrow down): Recheck CGM in 15 min; continue usual care
vi.	If CGM between 70-100 mg/dL and arrow direction: O or C : continue usual care
vii.	If CGM between 70-100 mg/dL and arrow direction: Horizontal - Recheck CGM in 30 min and follow research blood glucose protocol
viii.	If CGM between 70-100 mg/dL and arrow direction: Recheck CGM in 15 min and follow research blood glucose protocol
ix.	If CGM between 70-100 mg/dL and arrow direction: (1 arrow down) — Administer one of the following options and recheck CGM device 15 minutes after intervention and follow research blood glucose protocol again: 1. 4 oz. (120 ml) juice
	2. 1 glucose tablet

3. 1/2 tube glucose gel

- 4. 7.5 ml D50W IV
- x. If CGM between 70-100 mg/dL and arrow direction: (2 arrows down) \bigvee Administer one of the following options and recheck CGM device 15 minutes after intervention and follow research blood glucose protocol again:
 - 1. 8 oz. (240 ml) juice
 - 2. 2 glucose tablets
 - 3. 1 tube glucose gel
 - 4. 15 ml D50W IV
- xi. If CGM < 70 mg/dL: confirm with finger stick blood glucose and initiate standard of care per hospital hypoglycemia protocol per hospital policy. Resume CGM study research blood glucose protocol after two hours.

Additional standing orders in the Dexcom Gen6 protocol:

- a. Protocol will not encompass changes in basal, pre-meal, or corrective factor insulin ordered by the attending physician.
- b. Provide 24-hour CGM printout of glucose monitoring on morning rounds to the physicians caring for patients in the intervention group for their consideration in adjusting the scheduled basal/bolus insulin based on the CGM pattern. Information will also be provided regarding any interventions that were provided to the patient as a result of the research glucose protocol during the prior 24 hours.
- c. Review 24-hour CGM printout with patient in the intervention group to outline the effect of food, insulin and any exercise that may have occurred during the past 24 hours on glycemic control.

Usual Care for Glucose Control (Control condition): Patients assigned to the control condition will receive usual care as ordered by their attending physician. That means, the patient's glucose management will be based on reading from the blood glucose test that are conducted within a 24-hour period, and orders for glucose management will be determined by the attending physician.

Outcome Measures: Impact of CGM on key patient health indicators will be tracked during the enrolled patient's inpatient stay for up to 14 days. Number of events or amount of time will be calculated in consideration by the total time while the patient is hospitalized with an active Dexcom Gen6 device (i.e., total time in which the Dexcom Gen6 is in use will serve at the denominator). Patients with less than 48 hours of Dexcom Gen6 reading will be excluded from outcome data analyses. Key outcomes abstracted from the Dexcom Gen6 will include:

- 1) Episodes of hypoglycemia (two consecutive CGM reading above or below threshold)
- 2) Episodes of hyperglycemia (two consecutive CGM reading above or below threshold)
- 3) Episodes of severe hypoglycemia
- 4) Episodes of severe hyperglycemia/DKA
- 5) Total time spent in the target range of 100-180
- 6) Number of times that CGM readings would change management of hypoglycemia compared to standard care

Other outcome measures to be collected include:

- 1) Questionnaires regarding perceptions of use of CGM devices in the inpatient setting to be completed by nurses and physicians
- 2) Questionnaires about the anticipated experience and actual experience of wearing a CGM device by the patient. To be administrated by research nurse immediately prior to application of the device and immediately after removal of the final device applied (i.e., immediately prior to discharge)
- 3) Length of stay
- 4) The Diabetes Treatment satisfaction questionnaire-change (DTSQc) at completion of Dexcom Gen data collection (11)

Other variables to be collected and entered in the data analyses include:

- 1) Patient demographics
- 2) Medical history
- 3) Admitting diagnosis
- 4) Information about home diabetic regimen
- 5) Most recent hemoglobin A1c found in EHR
- 6) Length of time since diagnosis of diabetes
- 7) Any skin irritation at the site of monitor device insertion

Data Analysis: The proposed inpatient health indicators related to glucose management will serve as the study's primary outcomes. The primary outcome measures, number of hypoglycemic events and time in the target range, will be compared between two conditions using t-test. Non-parametric test (such as Wilcoxon-Mann-Whitney test) will also be used to examine unadjusted differences in the events between two groups if the distributional assumption of outcome measures does not meet the normality assumption. Other compounding variables such as patient demographics, admitting diagnosis, HbA1c will be adjusted where applicable. Statistical analyses will be conducted using SAS 9.2.

Other outcome measures on patient and provider's experience and perception of using CGM device and Diabetes Treatment Satisfaction Questionnaire-change (DTSQc) also will be analyzed. Specific analytic plan will be determined after the questionnaire is developed (See example of survey questions in Appendix).

Anticipated Challenges: The study team composed of clinical staff and research members is well prepared to carry out the proposed research. There are, however, potential challenges to completing the proposed research. The team is aware of these challenges and will be prepared to address challenges if they emerge. Potential challenges include:

- 1. Potential adverse effects of the device
 - a) Skin irritation, infections, bleeding etc.
 - b) Inaccurate sensor value
 - c) Error in entering the calibration code from the sensor that would require manual calibration
 - d) Patient annoyance due to device alarms
- 2. Clinical staff adherence to protocol
 - a) Nursing staff on the units will be trained in using Dexcom readings for treatment group patients. Specific components that will be addressed include:

- During 2 hr warm up nursing staff will use finger stick blood glucose for dosing decisions.
- In situations when the CGM is not showing a number value or arrow, a fingerstick blood glucose reading should be obtained.
- If patient symptoms do not correlate with CGM glucose values or if symptoms are indicative of hypoglycemia or hyperglycemia, a reading from the blood glucose meter will be obtained.
- Patients and caregivers should avoid the use of skin care products coming into contact with the Dexcom G6 CGM device.
- Patients, caregivers, and nurses should be aware that the transmitter and display device should be kept within 20 feet with no obstacles like walls or metal separating the patient location from the device location.
- Patients who receive Tylenol, over the recommended dose of 1000 mg/6 hrs will require a finger stick blood glucose .
- b) Attending physician on the units will be trained in using Dexcom readings for treatment group patients
- 3. Recording of CGM data for data analyses
- 4. Removal and replacement of CGM sensor to accommodate patients receiving CT or MRI.

If, as we assume, CGM is found to be a feasible practice for hospitalized patients, the team is prepared to move CGM into a practice innovation on the two units that participated in the pilot RCT. This will require further development of the RCT protocols into practice guidelines and ongoing training and monitoring of clinical staff implementation of CGM.

Anticipated benefits:

- 1. Intervention group
 - a. Improved glucose control in the target range of 100-180 mg/dL
 - b. Decreased severe hypoglycemic events
 - c. Decreased severe hyperglycemic events
 - d. Improved understanding of the trend of glucose readings over a 24-hour period and how these readings are affected by food, glucose, activity and stress
- 2. Control group
 - a. Realization of the patient's personal contribution to possibly improve medical practices for the larger population of inpatient patients with diabetes
 - b. Being allowed the experience of wearing a CGM device which may allow them to determine their personal interest in the use of such a device as an outpatient

Human Subjects:

Risks: The equipment used in magnetic resonance imaging (MRI), computed tomography (CT) scan, or high-frequency electrical heat (diathermy) treatment can potentially damage the Dexcom G6 CGM and produce inaccurate readings or prevent alerts, as a result. Therefore, subjects cannot wear the Dexcom G6 CGM (sensor, transmitter, receiver, or smart device) during those procedures. Subject in this study who need these procedures will have their CGM device removed prior to the test and replaced within twelve hours thereafter. There is potentially unknown risk to anyone who is pregnant, on dialysis, or critically ill,

as it is unknown how different conditions or medications used by these populations affect performance of the Dexcom G6 sensor. These populations are not included in this study. There is a risk of potential infection at insertion site if the site is not clean and completely dry. There is the potential of scarring or skin irritation if using the same insertion site too often. There is a risk of inaccurate reading of the Dexcom G6 due to taking higher than the maximum dose of acetaminophen (e.g. > 1 gram every 6 hours in adults). There is a risk that your personal information may be released outside of the study. Federal Privacy Regulations provide safeguards for privacy, security, and authorized access of your records.

Benefits: There is no monetary compensation to subjects in this study. The results of this study will provide generalizable data in regard to the care of hospitalized patients with diabetes with the use of continuous glucose monitoring (CGM) devices versus without the use of the CGM device. The knowledge and insight gained from this study will potentially change what is currently the standard of care for patients who require glucose monitoring.

Confidentiality: Participation in this study is voluntary. A potential subject's refusal to participate will not affect patient care. Proper precautions are in place to maintain a subject's confidentiality including limiting access to data to only key study personnel of the study and securing data via password-protected devices, locked filing cabinets, behind locked offices.

Informed Consent: Participants of this study will sign an IRB approved consent form. Trained and knowledgeable key study personnel (KSP) of the study will obtain informed consent.

Conflict of Interest Disclosure(s): All KSP will complete conflicts of interest disclosure. At this time, there are no identifiable conflicts to disclose.

Data Retention and/or Data Destruction Plan: All paper data related to the study will be stored securely in a locked file cabinet in a secured room. Any digital data files will be stored in a password protected BSWH maintained network. Access to data will be restricted to listed key study personnel only. Data abstracted for this study will be retained for study recordkeeping purposes and research compliance until the completion of the study. Once the study is closed, research related documents will be stored at the Dallas research Storage facility for an indefinite amount of time.

Subject Withdrawal:

Subjects may choose to withdraw from the study at any time prior to the conclusion of the study. Patients with less 48 hours of Dexcom Gen6 reading will be excluded from outcome data analyses.

Reporting adverse events or other significant events: Adverse events will be reported to the IRB accordingly and promptly.

Data collection:

Data will be collected for evaluation purposes and reported only in aggregate. Dexcom data will be compared to historical quality data reports of hypoglycemic events and hyperglycemic events on glucose management. Below is a list of variables that will be collected:

Table 1: Data Collection Variables							
Variable	Source						
Demographics							
MRN	EPIC						
Name (first, last)	EPIC						
DOB	EPIC						
Gender	EPIC						
Race	EPIC						
Ethnicity	EPIC						
Clinical Outcomes							
Admitting Diagnosis	EPIC						
Most recent hemoglobin A1C	EPIC						
Length of Stay	EPIC						
Episodes of hypoglycemic events	Dexcom						
Episodes of hyperglycemic events	Dexcom						
Total time spent in the target range of 100-180	Dexcom						

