Following randomization, the clinical nurse researcher will return to the patient's bedside to apply the Dexcom G6 or Dexcom G6 PRO sensor and transmitter. The sensor can be placed on the upper arm or abdomen. Those in the treatment group will then link the transmitter to the receiver. All clinical nurse researchers assigned to this project will be trained on the application of the device according to Dexcom protocol. The clinical nurse researcher will calibrate the device according to Dexcom protocol.

In some cases, patients will experience care procedures that require the device to be temporarily or permanently removed. If a patient requires a CT, the device will remain in place. If a patient requires an MRI as part of routine evaluation during hospitalization, the CGM device will be removed prior to imaging and a new one will be placed within twelve hours of the patient returning to their patient room on the nursing floor.

Dexcom sensors may be worn up to 10 days. The sensor will only be replaced if it is not providing appropriate readings or as noted above.

Standing Order for All Patients Enrolled in the Study:

Attending and/or consulting physicians will be responsible for writing orders for finger stick glucose measurements on all patients per standard care whether they are in the treatment or control group. Insulin orders will be determined by the patients' home medication history and current clinical status. To avoid investigator bias, orders written by the attending will not be adjusted by the study team with the exception of standing orders for nurse response to CGM readings as detailed below for those patients randomized to the treatment group. Standing orders for blood sugars <100 will allow for administration of glucose replacement in the treatment group based on Dexcom G6 reading.

CGM informed Clinical Care (Treatment Group):

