- 1) Test the health impact of CGM of inpatients as defined by rates of hypo- and hyperglycemia and the derivative of time in appropriate glucose range. Forty (40) patients will be randomized 1:1 into one of two conditions. In the treatment condition, patients will receive a Dexcom Gen6 device and the clinical staff (i.e., nursing and medical staff assigned to the patient's care) will be trained to use readings from the Dexcom Gen6 for the management of the patient's glucose levels below 100. In the control condition, patients will receive a Dexcom Gen6 device, but the clinical staff (i.e., nursing and medical staff assigned to the patient's glucose levels below 100. In the control condition, patients will receive a Dexcom Gen6 device, but the clinical staff (i.e., nursing and medical staff assigned to the patient's care) will not have access to the readings and will provide usual care (four glucose checks per 24 hours and use of insulin or other diabetic agent ordered by the admitting and rounding providers to determine glucose management).
 - a. Hypothesis 1: Patients in the treatment condition will experience fewer episodes of hypoglycemia as compared to patients in the control condition as measured by the Dexcom Gen6 readings.
 - b. Hypothesis 2: Patients in the treatment condition will experience less frequent hyperglycemia events as compared to patients in the control condition as measured by the Dexcom Gen6 readings.

Approach

Subject Recruitment & Enrollment Plan: Non-surgical, non-ICU patients with diabetes admitted to STC-3 and 6-North at BSWMC-Temple who meet the inclusion/exclusion criteria delineated below will be approached for enrollment within 24 hours of admission. Screening and enrollment will be conducted by a research nurse with consents signed for those wanting to participate.

Inclusion Criteria:

- Patients with Type 1 and Type 2 diabetes.
- Subjects greater than 18 years of age with diabetes.
- Subjects willing to avoid using high dose acetaminophen (defined as greater than 4 gm per day)
- Subjects with expected hospital length-of-stay of 2 or more days.
- Subjects willing to wear CGM device.

Exclusion Criteria:

- Female subjects who are pregnant or lactating at the time of enrollment into the study. Females with child bearing potential will be queried about the possibility of pregnancy and a serum pregnancy test will be performed.
- Subjects with greater than 4gm use of Tylenol/24 hr.

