- 1. The IRB will have the responsibility of determining if the overall study should be stopped. Each participant withdrawal (except withdrawal of consent) will be reported to the IRB within 3 days.
- 2. If an investigational device malfunction results in an SAE and the issue cannot be corrected by a modification to the system or a component of the system or adjustment to protocol procedures, the study will be stopped.
- 3. In the case of unanticipated adverse device effects (UADEs) related to a severe adverse event, the study will be stopped while the severe adverse event is evaluated and a root cause is determined by the Sponsor.

Randomization:

Patients that meet enrollment eligibility and consent to participate in the RCT will be randomized 1:1 to one of two conditions, treatment or control using Research Electronic Data Capture (REDCap). Randomization will be performed by assigning computerized random numbers. Computerized random numbers will be generated statistical software.

Application of the Dexcom Gen6 Device:

Following randomization, the clinical nurse researcher will return to the patient's bedside to apply the Dexcom Gen6 sensor and transmitter followed by linking the transmitter to the receiver for all enrolled patients (i.e, participants assigned to treatment and control). All clinical nurse researchers assigned to this project will be trained by [name] on the application of the device according to Dexcom protocol. The Clinical Nurse Researcher will calibrate the device according to Dexcom protocol.

In some cases, patients will experience care procedures that require the device to be temporarily or permanently removed. If a patient requires a CT or MRI as part of routine evaluation during hospitalization, the CGM device will be removed prior to imaging and a new one will be placed within twelve hours of the patient returning to their patient room on the nursing floor.

Dexcom Gen6 sensors may be worn up to 14 days. The sensor will only be replaced if it is not providing appropriate readings or as noted above.

Standing Order for All Patients Enrolled in the Study:

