Attending and/or consulting physicians will be responsible for writing orders for fingerstick glucose measurements on all patients per standard care whether they are in the intervention or control group. Insulin orders will be determined by the patients' home medication history and current clinical status. To avoid investigator bias, orders written by the attending will not be adjusted by the study team with the exception of standing orders for nurse response to CGM readings as detailed below for those patients randomized to the intervention group. Standing orders for blood sugars <100 will allow for administration of glucose replacement in the intervention group based on Dexcom Gen6 reading.

CGM informed Clinical Care (Treatment Condition):

Glucose management of patients in the treatment group will be guided by readings from the Dexcom Gen6. The Dexcom system will provide interstitial fluid glucose measurements at five-minute intervals used to construct a graph for trending CGM levels as well as an approximate rate of change. Threshold alarm for hypoglycemia will be set with CGM glucose values < 100 mg/dL and system alarm for CGM glucose value < 55 mg/dL. The alarms will be incorporated into the decision protocol for treatment of low blood glucose levels to achieve the stated goal of improved glycemic control and decreased rates of hypoglycemia within the hospital setting.

This requires a detailed protocol of how the devices is to be used in the RCT and that all clinical staff assigned to the patient be trained to follow the protocol (i.e., staff must be trained to use CGM as a patient care tool).

The Dexcom Gen6 protocol includes the following:

 The intervention group will have the data displayed with alarms set for glucose measurements of A. Threshold alarm CGM glucose < 100 mg/dL

B. The urgent low soon alert, indicated by 2 downward arrows on the device reading. (Blood sugar of 55 mg/dL in less than 20 minutes)

- C. Urgent low system alarm set at CGM glucose < 55 mg/dL.
- 2) Definition of target range is CGM glucose 100 -180 mg/dL
- 3) Definition of hypoglycemia is CGM glucose < 70 mg/dL (2 consecutive CGM readings below threshold)
- 4) Definition of hyperglycemia is CGM glucose > 300 mg/dL (2 consecutive CGM readings above threshold)
- 5) Definition of Severe hypoglycemia (see below)

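### The Combined protocol and SAP links a receiver for control patients without saying how its display and alarms are masked, and the Protocol contradicts it

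*Combined protocol and SAP*

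**What the plan says.** **Combined protocol and SAP.**

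- The AIM section gives both arms the same device: "In the control condition, patients will receive a Dexcom Gen6 device". It then says that the nursing and medical staff caring for control patients "will not have access to the readings and will provide usual care". No one else is named as masked.
- Application of the Dexcom Gen6 Device has the nurse researcher apply the sensor and transmitter, "followed by linking the transmitter to the receiver for all enrolled patients (i.e, participants assigned to treatment and control".
- CGM informed Clinical Care (Treatment Condition) says: "The intervention group will have the data displayed with alarms set for glucose measurements of" a list of low-glucose thresholds. No matching statement is made for control receivers.
- Usual Care for Glucose Control (Control condition) describes care ordered by the attending physician. It mentions no masked mode, covered screen, silenced alarm or custodian for the receiver.

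**Protocol.** The AIM section and the control-group care paragraph give controls a different device, the G6 PRO. Application of the Dexcom Devices limits pairing to one arm: "Those in the treatment group will then link the transmitter to the receiver". Its masking statement, like the other document's, names clinical staff only.

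**The concern.** The contrast under test is access to CGM information. In the Combined document the treatment package is not confined to staff, because the additional standing orders also have the 24-hour printout reviewed with the patient. Patient awareness of the readings is therefore part of the intervention.

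A control patient with a linked receiver in view could notice a low reading, eat something or call the nurse. Calling the nurse would also undo the staff masking, since the patient can pass the reading on. The two primary outcomes, number of hypoglycemic events and time in the target range, are the ones such leakage would affect. It would tend to make the arms look more alike, and it could not be removed at analysis.

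**Working it through.** No figure in the plan bears on this point, so the check is mainly a comparison of passages.

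**1. The two documents side by side**

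| Feature | Combined protocol and SAP | Protocol |
|---|---|---|
| Control device | Gen6, same as treatment | G6 PRO |
| Receiver linked for controls | Yes, stated explicitly | No, treatment group only |
| Who is denied control readings | Clinical staff | Clinical staff |
| Display and alarms | Assigned to the intervention group | Assigned to the treatment group |
| How a control display is hidden | Not stated | No control receiver is described |

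The linking sentence in the Combined document names both arms, so it cannot be read as covering the treatment arm alone. A nurse researcher following it links a control receiver and finds no instruction on its screen, alarms or location. The text available does not say which document is in force.

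**2. Illustration of size (assumptions, not plan figures)**

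Inputs from the documents: 40 patients randomized 1:1, so 20 per arm, with the primary outcomes compared by t-test. No alpha, power, effect size or standard deviation is given. Assumed here: two-sided 5% and a normal approximation. A share c of controls is assumed to gain the full CGM effect, so that the true difference becomes (1 − c) times its uncontaminated value. The exclusion of patients with under 48 hours of readings is ignored.

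- Difference detectable with 80% power: (1.960 + 0.842) × √(2/20) = 0.886 SD.
- Power at a diluted difference d: Φ(d × √(20/2) − 1.960).
- Number per arm to restore 80% power: 20/(1 − c)², rounded up.

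| c | Diluted difference (SD) | Power | Per arm for 80% |
|---|---|---|---|
| 0 | 0.886 | 80% | 20 |
| 0.10 | 0.797 | 71% | 25 |
| 0.25 | 0.664 | 56% | 36 |
| 0.50 | 0.443 | 29% | 80 |

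For example, at c = 0.25: 0.664 × 3.162 − 1.960 = 0.14, and Φ(0.14) is about 0.556.

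These rows show how dilution works in a trial of this size. They do not estimate what would happen here, because the documents give neither c nor the starting effect.

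**The case against.** **The plan intends control data to be hidden.** The Combined document assigns displayed data and alarms to the intervention group and denies control readings to staff. Linking a receiver is not the same as showing data or sounding an alarm. This stands as evidence of intent. What is missing is a procedure that carries it out, and any mention of the patient.

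**A reader might infer that a live, alarming display must sit in each control patient's room.** The documents do not support that. Nothing says that the control receiver is live. The range advice, that "the transmitter and display device should be kept within 20 feet with no obstacles like walls or metal separating" the patient from the device, is worded as a recommendation. It also falls in a list headed "Nursing staff on the units will be trained in using Dexcom readings for treatment group patients". A linked control receiver might plausibly need the same range, but that is inference.

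**The problem does not arise in the Protocol.** This is right for the receiver route, since no control receiver is described there. What remains in that document is narrower: its masking statement stops at clinical staff, and it does not say that the G6 PRO withholds readings from the wearer.

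**The dilution figures overstate the loss.** This is fair. They give every contaminated control the full CGM effect, whereas most of the package is delivered by staff through standing orders, timed rechecks and printouts to physicians. The starting effect is also not the trial's own, and the study is described as a feasibility pilot.

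**Deleting control linking could lose data.** This also stands. In the Combined document the key outcomes come from the Gen6, and linking to the receiver is the only step after application that the device section describes. Removing it without changing the control device could leave no described route to control outcomes.

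**Conclusion.** The point holds as a conflict between the documents together with a gap in masking. One document instructs that control patients be linked to a receiver and the other does not, and they name different control devices. Neither extends masking to the control patient or family, and the Combined document gives no means of hiding the control display and alarms.

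Contamination of the usual-care arm is possible if the linking step is followed as written. It is not shown to be certain, and a reader should not conclude that the comparator is already lost. If it occurred, the likely direction is a smaller difference in hypoglycemic events and time in range. This assumes that control patients who notice low readings act on them or report them. The size is unknown. The powers of 71%, 56% and 29% rest on an assumed contamination share, a full CGM effect in each contaminated control, and an effect size and alpha that the documents do not give.

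**What to change.** 1. Reconcile the AIM and device-application sections of the two documents. Align the Combined protocol and SAP with the Protocol's control device and with receiver linking in the treatment group only. The device and linking changes should be made together, so that control outcome data are not lost.
2. If a control receiver must still be linked to capture outcome data, state that its readings and alarms are hidden from the patient, family and treating staff. Name the role that holds it.
3. In both documents, extend the masking statement from clinical staff to the control patient and family.
4. Log any unmasking of a control patient or their staff, with the date and what was seen, and report the count by arm.

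The cost is wording in both documents, a small log, and confirmation of how control data are retrieved. The Protocol already contains most of the change.
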